The initial biopsy will already have been performed prior to enrollment into the study, demonstrating eligibility for inclusion. The process by which the specified distribution of lesions will be verified will be with transperineal or transrectal fusion targeted biopsy of lesion plus 10-14 core systematic biopsy to include adequate sampling of peripheral zone. Three-dimensional data on the location and specific grade for each lesion will be available and focal ablation planning will be based on this information. PSA for inclusion in the study is to have been performed prior to the initial biopsy, or it may be performed after biopsy as long as it is taken greater than 30 days after biopsy.

See **Appendix A – Standard Operating Procedure: 2. Transperineal and Transrectal Prostate Biopsies Protocol** for full details.

3.3 *Objectives*

3.3.1 *Primary Objectives*

- To determine the NanoKnife System's ablation effectiveness by measuring the negative in-field biopsy rate at 12 months.
- To determine the NanoKnife System's procedural and post-procedural safety profile by evaluating adverse event incidence, type, and severity through 12 months.

3.3.2 *Secondary Objectives*

- To evaluate urinary and erectile function after NanoKnife System treatment using validated subject questionnaires (UCLA-EPIC, IPSS, IPSS-QOL, IIEF-15).
- To determine post-NanoKnife System treatment prostate-specific antigen (PSA) kinetics, including time to PSA nadir and post-nadir PSA stability.
- To determine the change in prostate volume by comparison of prostate volume measured on multiparametric MRI (mpMRI) pre-treatment and at 12 months post-treatment.
- To determine the effectiveness of therapy by assessing the need for secondary or adjuvant treatment following therapy.
- To determine health-related quality of life (HRQoL) levels after treatment with the NanoKnife System using a validated subject questionnaire (EQ-5D).

3.4 *Hypotheses*

The primary efficacy analysis will be the rate of subjects with a negative in-field biopsy at 12 months. The rate of negative in-field biopsies will be compared to a performance goal of 0.52 using a one-sample non-inferiority test for proportions.

The null and alternative hypotheses for negative biopsy rate at 12 months are as follows:

H_0 : NanoKnife System \leq (0.61 – margin of 0.09)

H_1 : NanoKnife System $>$ (0.61 – margin of 0.09)

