6.5 Subject Disposition

All subjects undergoing treatment as part of this study will be included in analyses, including those subjects for which treatment could not be completed due to adverse events or other complicating factors. Subjects will be followed for a maximum of 12 months, unless a subject has unresolved AEs, in which case they will be followed until all AEs are resolved or are determined to have no resolution, and disposition of all these subjects will be presented, including those completing follow-up and those

excluded due to treatment failure, adverse events, withdrawal by the subjects or Investigator, and those lost to follow-up.

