8.5 Subject Compliance

Subjects' participation in the study will terminate when they either complete the 12-month follow-up visit or discontinue participating in the study prior to completion. The reason for the subject's termination from the study will be documented on the Termination CRF. Upon study completion or termination, each subject will be instructed to visit his referring physician for evaluation and monitoring and/or treatment following the best practice guidelines for intermediate risk subjects.

Subjects may voluntarily withdraw from the study at any time, but a physician cannot arbitrarily remove a subject from the investigation. The reason for all subject withdrawals should be documented. If a subject is withdrawn from the study, every effort will be made to continue to follow the subject for safety, including the use of phone calls (up to three) and couriered mail, to obtain safety follow-up information.

Subjects will be required to meet the follow-up visit schedule outlined in *Table 4-4*.

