6.1 Changes from Protocol

There are no plans to further the follow-up beyond the 12 months. The continuation of follow-up for up to 5 years, as standard of care, to assess the rate of progression, re-intervention, and adverse events is not expected at this point. This exploratory endpoint stated in protocol is outside of the scope of this SAP.

No multiple imputation will be used for the missing items for 15-Item International Index of Erectile Function (IIEF-5), International Prostate Symptom Scores (IPSS), and Expanded Prostate Cancer Index Composite (EPIC) questionnaires, as stated in the protocol.

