12.7.7 Assessment of Ablation Effectiveness by Evaluation of Prostate Tissue by mpMRI

The number and proportion of subjects determined to have cancer-bearing prostate tissue lesions (i.e., modified prostate imaging reporting and data system [PI-RADS] 3 or higher lesion) on the 3 and 12-month mpMRI will be presented.

12.7.8 Assessment of Need for Secondary or Adjuvant Treatment Following Treatment with the NanoKnife System

The number and proportion of subjects undergoing secondary or adjuvant treatment during the study will be presented. Additional information regarding reason (positive unscheduled biopsy [in-field or out-of-field], clinical progression, biochemical progression, or other), location (index lesion or contralateral lesion), and type of re-retreatment (re-treatment with IRE, radical prostatectomy, high-intensity focused ultrasound [HIFU], cryotherapy, or other) will also be presented.

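### The need for secondary or adjuvant treatment is counted only up to study exit at the 12-month visit, so treatment prompted by that visit's biopsy or mpMRI will almost never be counted

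*Combined protocol and SAP*

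**What the plan says.** Protocol 3.3.2 states the objective: "To determine the effectiveness of therapy by assessing the need for secondary or adjuvant treatment following therapy". SAP 7.2 repeats it.

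The analysis, in SAP 12.7.8 and in the same terms in protocol 6.9, is: "The number and proportion of subjects undergoing secondary or adjuvant treatment during the study will be presented". The SAP adds a breakdown by reason: "Additional information regarding reason (positive unscheduled biopsy [in-field or out-of-field], clinical progression, biochemical progression, or other". The scheduled 12-month biopsy is not named as a reason.

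On when a man leaves the study, protocol 8.5 says "Subjects' participation in the study will terminate when they either complete the 12-month follow-up visit or discontinue participating in the study prior to completion", and that at exit "each subject will be instructed to visit his referring physician for evaluation and monitoring and/or treatment". Protocol 6.5 agrees: "Subjects will be followed for a maximum of 12 months, unless a subject has unresolved AEs".

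The schedule (protocol Table 4-4, SAP Table 1) puts the only biopsy planned for every man at the 12-month visit, together with the second of two scheduled post-treatment mpMRIs. Earlier biopsies are for cause: a lesion of PI-RADS 3 or higher at 3 months, a PSA rise meeting the Phoenix definition, or clinical suspicion (protocol 4.6.16).

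Protocol 3.5.3 and 6.10 include an exploratory five-year re-intervention endpoint drawn from medical records. SAP 6.1 says "There are no plans to further the follow-up beyond the 12 months" and places that endpoint outside its scope.

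**The concern.** Need and receipt differ when the observation window closes at the moment the main diagnostic result is obtained. A man whose cancer is first found at his scheduled 12-month biopsy has had no opportunity to receive further treatment inside the study. He is sent to his referring physician, and whatever follows is not collected for this endpoint.

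He nevertheless remains in the denominator. The reported percentage then reflects mainly treatment prompted by the 3-month mpMRI, a PSA rise or clinical suspicion. Presented as an answer to the objective on need, it would be too low, and the error runs one way, in favour of the device.

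**Working it through.** **Timing**

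1. Numerator: men who undergo further treatment during the study (SAP 12.7.8, protocol 6.9).
2. Exit: on completing the 12-month visit, window 365 ± 28 days (protocol 8.5, Table 4-3).
3. The scheduled biopsy and second mpMRI are done at that same visit, and pathology is reported afterwards.
4. Treatment prompted by those results therefore falls after exit, unless the tests are done early in the window and treatment is given before the visit is formally complete. Almost never is accurate; never would not be.
5. Denominator: SAP 12.7.8 does not state it. The ITT population is inferred from SAP 12.7.

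**Inputs for size**

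- Assumed negative in-field biopsy rate 0.69; drop-out 15%; 100 subjects inflated to 118 (protocol 6.2, SAP 8.1).
- Missing biopsies are imputed as positive (protocol 6.4, SAP 10.6).
- Not in the documents: the share of positives first found at 12 months (f), and the share of those who are then treated (t). Both are taken as 0.5 to 0.8, as assumptions.

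**The plan's own figure.** No rate is stated for this endpoint. The enrolment figure reproduces: 100 / (1 − 0.15) = 117.6, rounded up to 118.

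**Men with a positive in-field biopsy**

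- Low: 118 × 0.31 = 36.6 failures. If all 118 × 0.15 = 17.7 drop-outs lie inside that 31%, then 36.6 − 17.7 = 18.9, about 19 men.
- High: 31% of 100 evaluable men = 31 men.

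**Men treated but not counted = positives × f × t**

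- Low: 19 × 0.5 × 0.5 = 4.75; 4.75 / 118 = 4.0%.
- High: 31 × 0.8 × 0.8 = 19.8; 19.8 / 118 = 16.8%.

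**Sensitivity to f, before any treatment rate is applied**

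- If 75% of positives are found early (f = 0.25): 18.9 × 0.25 = 4.7 to 31 × 0.25 = 7.8 men (4.0% to 6.6% of 118) are first found at 12 months.
- If none are found early (f = 1): 18.9 to 31 men (16.0% to 26.3%).

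**Illustration.** With 31 positives and a quarter found early (assumed), the endpoint could show at most 7.8 / 118 = 6.6% treated on an early positive in-field biopsy, against 31 / 118 = 26.3% biopsy-positive.

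These counts cover in-field disease only. Protocol 4.6.16 also allows a 12-month biopsy outside the treated area if the MRI shows something new or a suspicious change; treatment following from that would be missed as well.

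**The case against.** The best defence is that the disease itself is not hidden. A positive 12-month in-field biopsy is a primary-endpoint failure, with Gleason total score detailed (SAP 12.7.1). The Delphi-criterion analysis details Gleason score for its positives too (SAP 12.7.2), and lesions of PI-RADS 3 or higher on the 12-month mpMRI are tabulated (SAP 12.7.7). Only the treatment that follows is missing, from an endpoint the protocol says it is not powered to support claims on. All of this stands, and it limits the consequence.

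Several stronger readings are tempting but not supported:

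- *The 12-month tests trigger most further treatment.* The documents give no split between early and 12-month detection. The 3-month mpMRI is also scheduled for every man, and PSA is drawn at five follow-up visits.
- *The SAP declares the uncounted men not to need treatment.* It reports who underwent treatment and says nothing of the rest. The fault is a mismatch between objective and measure.
- *The reason list proves that scheduled-biopsy cases are excluded.* It ends with a residual category that could hold them. Exclusion comes from the timing of exit.
- *Five-year re-intervention has been abandoned.* SAP 6.1 says it is not expected at this point and puts it outside the SAP; the protocol retains it.
- *As many as 24 men, or 20 points, could be missed.* That needs 37 positives (37 × 0.8 × 0.8 = 23.7), hence no drop-out, against the plan's own 15%.

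Two further cautions hold. Not every positive biopsy leads to treatment: the primary endpoint's positives can include small Gleason 6 foci that the Delphi criterion calls insignificant, which the 50–80% treatment assumption only partly allows for. And the CRF is not reproduced, so one cannot confirm that a suitable field is absent.

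**Conclusion.** The point holds. As written, the plan measures treatment received up to study exit and offers it as the answer to an objective on need. Treatment arising from the 12-month biopsy or mpMRI will almost never be counted, so the figure understates need in the device's favour.

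The truncation follows from the documents alone. Its size does not: 5 to 20 men (4 to 17 percentage points of 118) rests on the 69% planning assumption, on how drop-outs overlap with failures, and on the two assumed 50–80% ranges. Only men first found positive at 12 months are affected; a man already re-treated earlier is counted.

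The primary analysis is untouched. This should be corrected because the endpoint would mislead under its present name, but it does not threaten the trial's main conclusion.

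**What to change.** In SAP 12.7.8 and protocol 6.9:

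1. Report (a) secondary or adjuvant treatment received, labelled as received through the 12-month visit and not as need.
2. Report separately (b) further treatment recommended or planned by the treating physician on the 12-month biopsy or mpMRI, recorded on the Visit 8 or termination CRF once pathology is back, with a stated rule for when the entry is made. Give the total of (a) and (b), counting each man once.
3. Add a positive scheduled 12-month biopsy to the reason list.
4. Cross-tabulate (a) and (b) by 12-month biopsy result.
5. State the denominator.

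Also reconcile protocol 8.4, which requires additional consent to review source documents collected after close-out, with protocol 4.6.16 and 6.10, which say record access through five years will be allowed.

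The cost is about one CRF field (subject to what the CRF already holds) and revised wording, with no extra visit or procedure. A planned treatment is softer evidence than a received one in an unblinded study, so both must be shown. The reported need will look less favourable.

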12.7.9 Evaluation of Subject-Reported Quality of Life

For the purpose of assessing Quality of Life (QoL), the EQ-5D® will be used. Summary statistics will be presented for the timepoints where the questionnaire is collected (baseline, 1, 3, 6, 9, and 12 month follow-up).

The questionnaire has 5 dimensions from a descriptive system (Mobility, Self-care, Usual activities, Pain/discomfort, and Anxiety/depression), described in [Table 16](#), and a visual analogue scale (VAS) related to subject's self-rated health.

Table 16 EQ-5D dimensions on descriptive system

Dimensions	Possible answers	Item Response Level
Mobility	I have no problems in walking about	1
	I have slight problems in walking about	2
	I have moderate problems in walking about	3
	I have severe problems in walking about	4
	I am unable to walk about	5
Self-care	I have no problems washing or dressing myself	1
	I have slight problems washing or dressing myself	2
	I have moderate problems washing or dressing myself	3
	I have severe problems washing or dressing myself	4
	I am unable to wash or dress myself	5
Usual activities	I have no problems doing my usual activities	1
	I have slight problems doing my usual activities	2
	I have moderate problems doing my usual activities	3
	I have severe problems doing my usual activities	4
	I am unable to do my usual activities	5
Pain/discomfort	I have no pain or discomfort	1
	I have slight pain or discomfort	2
	I have moderate pain or discomfort	3
	I have severe pain or discomfort	4
	I have extreme pain or discomfort	5
Anxiety/depression	I am not anxious or depressed	1
	I am slightly anxious or depressed	2
	I am moderately anxious or depressed	3
	I am severely anxious or depressed	4
	I am extremely anxious or depressed	5

Each dimension answered will be associated with a level, from 1 to 5, as detailed in [Table 16](#). The levels are the levels of perceived problems:

- Level 1: Indicating no problem;
- Level 2: Indicating slight problems;
- Level 3: Indicating moderate problems;
- Level 4: Indicating severe problems;
- Level 5: Indicating unable to/extreme problems.

A unique health state is defined by combining one level from each of the five dimensions. It allows 3123 possible health states, where each state is referring to a 5-digit code. No total score will be presented for the EQ-5D. The unique health state for a subject will only be presented in a listing.

The EQ VAS asks how the subject would rate their health that day (i.e., “Your Health Today”). The answer is a quantitative value that ranges from 0 to 100, where 100 means best health possible the subject can imagine and 0 means the worst health the subject can imagine ([Oppe et al., 2014](#), [van Reenen et al., 2019](#)). Summary statistics of the EQ VAS score will be presented for each timepoint. Additionally, change from baseline for all the follow-up timepoints of the EQ VAS scores will also be presented.

12.7.10 Sensitivity Analyses

All efficacy analysis will be repeated for the PP population. Additionally, a sensitivity analysis in the ITT population will be performed for the primary efficacy endpoint by only including subjects with biopsy data available at 12-months or who has a positive in-field biopsy prior to 12-months (i.e., without performing missing data imputation for subjects with missing biopsy information post-ablation).

12.8 Safety Analyses

All safety analyses will be presented for the ITT population. If a subject is re-treated with something other than the NanoKnife System during the study, the subject should exit the study; any safety data collected during and after the re-treatment will not be included in the safety analyses. Further, if a lesion is re-treated with the NanoKnife System more than once during the study, the subject should exit the study; any safety data collected for a subject after the second re-treatment of the same lesion will not be included in the safety analyses.

12.8.1 Adverse Events

All AEs reported by the sites will be recorded in the EDC. All AEs that meet the criteria for adjudication will be reviewed by the adjudication committee. For the events that are adjudicated, the adjudicated data will serve as the primary data source for analysis purposes. The site-reported AE data will be used for analysis of AEs that do not meet the criteria for adjudication.

A summary of all AEs will be presented, including the number of events and number and percentage of subjects reporting adverse events in the following categories: any AE (including 95% CI for the proportion), any severe AE, any ADE, any AE leading to death, any SAE, and any AE leading to study discontinuation.

A

A breakdown of the number of events and the number and percentage of subjects reporting each AE, categorized by body system and preferred term coded according to the MedDRA dictionary, will be presented. Note that the counting of subjects with each event will be by subject rather than by event so that subjects are only counted once within each body system or preferred term.

A further tabulation of these data, categorized by relationship to NanoKnife System treatment, will be presented. When counting the number of subjects with each event, subjects with multiple events within a particular body system or preferred term will be counted under the category of their most procedure-related event within that body system or preferred term. Relationship to NanoKnife System treatment is categorized as: i) not related (“The cause of the AE is known and is not related to any aspect of study participation including the underlying condition”), ii) reasonably possibly related (“There is a reasonable possibility that the event may have been caused by study participation. The AE has a timely relationship to the study procedure(s); however, it follows no known pattern of response and an alternative cause seems more likely or there is significant uncertainty”), iii) probably related (“It is probable that the event was caused by study participation. The AE has a timely relationship to the study procedure(s) and follows a known pattern of response, but a potential alternative cause may be present.”), iv) definitely related (“The event was definitely related to study participation. A related event has a strong temporal relationship and an alternative cause is unlikely.”), or v) unknown as recorded on the CRF.

A summary of events reported, categorized by severity (Mild [Grade 1], Moderate [Grade 2], Severe or medically significant but not immediately life-threatening [Grade 3], Life-threatening consequences [Grade

4], and Death [Grade 5]), will also be provided. Grades are determined according to CTCAE severity grades. When counting the number of subjects with each event, subjects with multiple events within a particular body system or preferred term will be counted under the category of their most severe event within that body system or preferred term.

All AEs recorded on the CRF will be provided in a listing. Independent listings will be provided with MedDRA system organ class (SOC), preferred and Verbatim terms for AEs, AEs with outcome of death, AEs leading to study discontinuation, and AEs related to NanoKnife treatment leading to study discontinuation.

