6.4 Missing Data

The following imputation methods will be used for the primary analysis of all endpoints:

- When calculating the proportion of subjects with a negative in-field biopsy, subjects with missing biopsy information post-ablation will be imputed as “positive”
- Subjects with missing pre- or post-ablation prostate volume measurements will be imputed as having a zero change in volume
- Missing PSA data will be imputed using last observation carried forward (LOCF)
- Missing data for IIEF-5, IPSS and EPIC questionnaires will be imputed using a multiple imputation approach at the item/question level.

All other endpoints/data (e.g., safety events) will be analyzed based on available (non-imputed) data, unless specified otherwise.

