6.8 Primary Safety Endpoint

The primary safety endpoint is the incidence of adverse events by type and CTCAE v5.0 severity through 12 months. The number and proportion of subjects who experienced at least one adverse event will be summarized, and the 95% confidence interval of the proportion will be presented.

If a subject is re-treated with something other than the NanoKnife System during the study, safety data collected during and after the re-treatment will not be included in the safety analyses.

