9.0 Endpoints

9.1 Primary Endpoint

The primary treatment outcomes that will be evaluated are:

- Rate of negative in-field biopsy at 12 months – determine the rate of subjects obtaining a negative in-field biopsy on follow-up transperineal or transrectal biopsy at 12 months.
- Incidence of adverse events by type and Common Terminology Criteria for Adverse Events (CTCAE) v5.0 severity through 12 months – determine incidence, type, and severity during the NanoKnife System procedure and through follow-up.

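### The adverse-event tables pool all onsets over 0–12 months and ignore unequal follow-up, so the post-procedural part of the primary safety objective is not shown separately and late events are modestly understated

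*Combined protocol and SAP*

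**What the plan says.** Protocol 3.3.1 states the primary safety objective as the "procedural and post-procedural safety profile by evaluating adverse event incidence, type, and severity through 12 months". SAP 9.1 words the endpoint in the same two parts: "determine incidence, type, and severity during the NanoKnife System procedure and through follow-up".

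For analysis, Protocol 6.8 gives one summary measure: "The number and proportion of subjects who experienced at least one adverse event will be summarized", with a 95% confidence interval. SAP 12.8.1 goes further. It plans an overall summary, "including the number of events and number and percentage of subjects reporting adverse events in the following categories". There are six of these: "any AE (including 95% CI for the proportion), any severe AE, any ADE, any AE leading to death, any SAE", and adverse events leading to discontinuation. The SAP then plans a table "categorized by body system and preferred term coded according to the MedDRA dictionary, will be presented", one by relationship to NanoKnife treatment and one by CTCAE grade. SAP 12.8.2 adds tables of SAEs and treatment-related SAEs.

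On the analysis set, SAP 12.8 says "All safety analyses will be presented for the ITT population", which means every man in whom a probe was inserted (SAP 9.3.2). On missing data, Protocol 6.4 says "All other endpoints/data (e.g., safety events) will be analyzed based on available (non-imputed) data". Protocol 6.8 and SAP 12.8 exclude safety data collected during and after re-treatment with another modality. SAP 12.8 also excludes data after a second NanoKnife re-treatment of the same lesion. The onset date of each event is recorded (Protocol 5.1).

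**The concern.** There are two gaps.

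First, the objective names two phases, and no table in SAP 12.8.1 or 12.8.2 is split by time of onset. Relatedness does not fill the gap. It is a causal scale, and an event on day 1 and an event in month 8 can both be definitely related. Frequent, short-lived events around the procedure can dominate a pooled percentage and hide what happens later.

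Second, follow-up will be unequal, and no adverse-event analysis allows for it. No person-time, Kaplan-Meier or cumulative-incidence method is given for harms. The sizing allows for 15% loss to follow-up; the analysis does not. The exclusion of safety data at re-treatment has the same effect: nothing removes those men from the ITT set or censors them. That cut may also be informative, because re-treatment can follow a positive early biopsy (Protocol 4.6.16).

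At stake is the late-event incidence through 12 months, which a reader would take as an estimate of the 12-month risk.

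**Working it through.** **Inputs from the documents.** Drop-out allowance 15%; 100 men needed for safety and 118 enrolled; true event rate 1.6%, with more than 80% chance of seeing at least one event (Protocol 6.2, SAP 8.1). The documents give no timing for events or drop-outs, so all timings below are assumptions. Drop-out is taken as independent of risk.

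**1. The plan's own figures.** 1 − (1 − 0.016)^100 = 80.07%, and 100/(1 − 0.15) = 117.6, so 118. Both reproduce.

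**2. Share of late events captured.** Let 15% of men leave evenly over 0–12 months. A man whose event would occur at month t has left beforehand with probability 0.15 × t/12. The captured share is therefore 1 − 0.15 × (mean event time)/12.

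| Events spread evenly over | Mean time (months) | Captured share |
|---|---|---|
| months 1–12 | 6.5 | 1 − 0.15 × 6.5/12 = 0.919 |
| months 3–12 | 7.5 | 1 − 0.15 × 7.5/12 = 0.906 |
| months 6–12 | 9 | 1 − 0.15 × 9/12 = 0.888 |

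**3. Adding the cut at re-treatment.** Suppose a further 5% or 10% of men have their data cut evenly over months 3–6; these rates are invented for illustration. For an event spread evenly over months 3–12, the chance that it falls after the cut averages (12 − 4.5)/9 = 0.833. The captured share drops by 0.05 × 0.833 = 0.042 or 0.10 × 0.833 = 0.083, from 0.906 to 0.865 or 0.823.

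**4. Effect on a whole 12-month risk.** Crude proportion = 0.85 × F(12) + 0.15 × (mean of F at the time of leaving), where F(t) is the cumulative risk by month t. Take a true 12-month risk of 10%, with a constant hazard for the part not placed at the procedure:

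- No risk at the procedure, even drop-out: 9.26%, about 7% low in relative terms.
- No risk at the procedure, all drop-outs leaving straight after it (worst case): 0.85 × 10% = 8.5%.
- 90% of the risk at the procedure, even drop-out: 9.93%, under 1% low.

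**5. Safety sizing under drop-out.** In the no-procedural-risk scenarios, a true rate of 1.6% is seen as 1.36% (worst case) to 1.48% (even drop-out). With 118 men the chance of at least one event is 1 − (1 − 0.0136)^118 = 80.1%, or 82.8% with even drop-out. The stated 80% is kept.

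**The case against.** Five arguments on the other side carry weight.

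- The wording of the objective may describe only the period of collection and not promise a table by onset. The endpoint is incidence by type and severity, which the planned tables deliver. This reading is possible, but it leaves the later profile unreported as a summary.
- Timing can be recovered, because all adverse events are listed. Urinary and erectile scores are also tabulated by visit (SAP 12.7.3, 12.7.4), so functional harm is shown over time. Both stand, but a listing is not an estimate, and the scores do not cover other harms.
- Withdrawn men are still to be contacted for safety (Protocol 8.5), so 15% is an allowance and not an expected loss of all safety data. This stands, and the true effect may be smaller.
- No safety hypothesis is tested, and the bias is small beside sampling error: 10 events in 118 men is 8.5%, with an exact 95% interval of 4.1% to 15.0%. This stands.
- Kaplan-Meier is specified for PSA nadir because time to nadir is a named endpoint, so its absence for harms is no inconsistency. This stands too.

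A reader might infer that the primary safety result is a single crude proportion in which drop-outs count as event-free. The documents do not support that. The SAP plans several tables by category, term, relatedness, grade and seriousness. An event recorded before a man leaves is counted; only later, unobserved events are lost. The ITT denominator is itself inferred from the analysis set, since the SAP states none for adverse-event percentages.

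**Conclusion.** The point holds in a limited form. No planned table separates procedural or peri-procedural onset from later onset, although the primary objective names both. No adverse-event analysis allows for early exit or for the data cut at re-treatment. If the denominator is all ITT men, as it appears, late-event incidence is understated: about 92% is captured over months 1–12 and 89% over months 6–12, with 15% drop-out spread evenly and unrelated to risk. The lower figures of 0.865 and 0.823 depend on assumed re-treatment rates and should not be read as forecasts.

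It would go too far to say that the headline any-AE proportion is materially biased or that the safety sizing fails. If most events are procedural, the former hardly moves, and the latter holds at 80.1% or better in the scenarios checked. That insensitivity is also why the later phase needs its own table: the pooled figure cannot reveal it. This is an inexpensive improvement that lets the trial report what its objective names.

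**What to change.** Amend SAP 12.8.1 and 12.8.2 as follows, keeping the crude tables.

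1. Add an adverse-event table by onset window, for example procedure through the 1-month visit, and after that visit through 12 months, with the cut set by the sponsor. State the denominator as men under observation at the start of each window. SAP 10.2 gives a change in severity or relationship a new start date and a new record; such a record must not count as a new late onset. State how events after a permitted NanoKnife re-treatment are assigned.
2. For Grade 3 or higher events, SAEs and ADEs, add the 12-month cumulative incidence with a 95% confidence interval. Censor at loss to follow-up and at the point where safety data are excluded for re-treatment, and treat death as a competing event. Note that censoring at re-treatment may be informative.

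The second item is needed because the first corrects little of the follow-up problem. With even drop-out only 15% × 1/12 = 1.25% of men have left by month 1, so the new denominator raises capture over months 1–12 only from 0.919 to 0.91875/0.9875 = 0.930.

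The cost is SAP wording and two tables from data already collected. Late-event rates would look slightly higher.
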